## Study Synopsis

Study Title	Utilizing Holmium Laser for FURS Renal Stone Lithotripsy Comparing Stone Breaking vs. Stone Dusting Settings	
Protocol No:	LUM-SBU-VP-15-01	
Device Name:	Lumenis Pulse 120H Holmium Laser system	
Design	Prospective, randomized, single center	
Planned Study period	Initiation: January 2016	Final Report: May 2016
Objective	Primary: Demonstrate the efficiency of stone dusting Vs stone breaking of the P120H holmium laser and 200 DFL ball tip fibers Secondary: Demonstrate the usability and safety of stone dusting	
Study population	Twenty (20) subjects presenting with a renal stone and candidates for FURS	
Main Inclusion Criteria	

Subject will be older than 18 years of age

Subject was diagnosed with renal calculi between 0.8 to 2 cm in size

Subject is a candidate for FURS procedure

Subject is willing and has signed the Informed Consent Form

	
Main Exclusion Criteria	

Underwent previous PCNL or FURS in current kidney

Need to perform concomitant procedure, other than FURS

	
Investigational Treatment and study course	
A single FURS procedure will be performed with either high or low frequency holmium laser lithotripsy. Subjects will be randomized during enrollment to receive treatment with one of the two parameter sets.
 
Follow up sessions:
 

Day of discharge

One month follow-up

	
Criteria for Evaluation (endpoints)	
Primary Endpoints:
 

Procedure time

Usage of alternative stone extracting devices

Catheterization time

Time to hospital discharge

Stone clearance based on 1 month follow-up imaging data

 
Secondary Endpoints:
 

Intraoperative Complications – based on Modified Clavien Classification

Visibility during procedure

Occurrence of retropulsion that interferes with procedure

Ability to reach fragments during the procedure

Fiber flexibility with scope deflection- any damage to fiber

Fiber durability- deflection without losing energy/ efficiency

Damage to scope

	

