## 6 Patient Population

### 6.1 Source and Sample Size

Subjects shall be selected by the physician within his patient population. One (1) site will participate in this study and will treat twenty (20) subjects. Enrolled subjects that did not complete the full course of the study will be discarded from performance analysis if they have not returned for the one month follow-up visits.

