### 7.3.3 Subject randomization

Allocation of the treatment parameters used during the procedure will be performed using study randomized envelopes. The sponsor will provide the site with sealed envelopes containing "stone breaking" or "stone dusting" treatment parameters. Randomization will be divided into two groups of patients (1-10 and 11-20) with randomization ratio of 1:1 in each group. The randomization list will take into consideration additional subjects that will be required to replace subjects that have dropped from the study. If any subject drops out from the study and is replaced by another subject randomization will continue as per the original randomization scheme (this new subject will not receive the randomization of the subject that was replaced).

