## **10.4 Subject Withdrawal/Dropouts**

The subjects will be advised in the written Informed Consent form that they have the right to withdraw from the study at any time without prejudice, and may be withdrawn at the Investigator's/Lumenis' discretion at any time. In the event that a subject drops out of the study or is withdrawn from the study, the Exit/Termination CRF should be completed. On the withdrawal page the Investigator should record the date of the withdrawal, the person who initiated withdrawal and the reason for withdrawal.

Reasonable effort should be made to contact any subject lost to follow-up during the course of the study in order to complete assessments and retrieve any outstanding data and study supplies. The records of subjects who terminate prior to completing the study will be retained and the reason for termination will be documented.

The following are possible reasons for subject dropout/withdrawal:

Utilizing Holmium Laser for FURS Renal Stone Lithotripsy Comparing  
Stone Breaking vs. Stone Dusting Settings

DOC No.: 1005553  
Revision: A  
State: under review  
ECO No: GEN-0006361

- Adverse event that would prevent subject compliance with the protocol;
- Subject withdrawal of consent;

However, every effort should be made to see that subject is followed for the remainder of the study even if subject is unable or unwilling to comply with the protocol.

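### Replacement of dropouts is not limited to those who leave before lithotripsy; with discretionary withdrawal and the 1-month discard rule, results already known can influence who is analysed

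*Combined protocol and SAP*

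**What the plan says.** Three sections of the combined protocol and SAP bear on this.

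- **Section 7.3.3 (randomization).** Spare allocations are planned: "The randomization list will take into consideration additional subjects that will be required to replace subjects that have dropped from the study". For the replacement itself: "If any subject drops out from the study and is replaced by another subject randomization will continue as per the original randomization scheme". The replacement takes the next envelope, not the arm of the subject who left. No limit is set by timing, reason or number.
- **Section 10.4 (withdrawal).** Subjects "may be withdrawn at the Investigator's/Lumenis' discretion at any time". Two possible reasons are listed: an adverse event that prevents compliance, and withdrawal of consent. The date, initiator and reason must be recorded, records are retained, and "every effort should be made to see that subject is followed for the remainder of the study". The section does not say how a withdrawn subject's data are analysed.
- **Section 6.1 (sample size).** "One (1) site will participate in this study and will treat twenty (20) subjects". Enrolled subjects who do not complete the study and do not attend at 1 month are removed from the performance analysis.

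No all-randomized or all-treated analysis set is defined. Allocation precedes surgery (Synopsis: "Subjects will be randomized during enrollment to receive treatment with one of the two parameter sets").

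**The concern.** Replacing a subject who leaves before treatment is harmless to the comparison, provided that the exit is reported. Replacing one who leaves after treatment is different, because by then some of that subject's results exist. The operating investigator applies the randomized laser settings (section 7.6.2) and so knows the arm. The sponsor, which supplies the device and the envelopes, shares the power to withdraw. Section 8.2 also has immediate post-operative data analysed after at least 10 surgeries, while later subjects can still be withdrawn and replaced.

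At stake is whether the analysed groups are still the randomized groups. If treated subjects with poor early results are more likely to leave, the comparison is biased. Substitution can then bring the analysed number back to 20, so that the loss is not visible from the count.

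**Working it through.** **1. Can a replaced dropout be a treated subject?** The documents never say so outright; it follows from three points. Section 7.3.3 has no timing limit. Section 10.4 allows withdrawal at any time and names an adverse event as a reason, while Table 1 starts adverse event assessment in the perioperative period. The non-completers of section 6.1 are defined by a missed 1-month visit, which takes in subjects who had surgery.

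**2. What is known by then?** The window runs from surgery to the 1-month visit, which ends participation (section 7.1).

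| Primary endpoint (section 5.1) | Known in that window? |
|---|---|
| Procedure time | Yes, at the end of surgery |
| Use of extraction devices | Yes, at the end of surgery |
| Time to discharge | Usually, within the hospital stay |
| Catheterization time | Depends on when the catheter is removed |
| Stone clearance on 1-month imaging | No |

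**3. How do the known results leave the analysis?** Withdrawal alone does not remove them. They leave through section 6.1: a withdrawn subject who does not return is dropped from the performance analysis as a whole, including endpoints measured weeks earlier. Section 7.3.3 then supplies a substitute. With two such subjects, 20 + 2 = 22 would be treated and 20 analysed.

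**4. How large could the effect be?** The sample size of 20 comes with no effect size, SD, power or dropout rate, so it cannot be reproduced. The only usable inputs are the allocation ("Randomization will be divided into two groups of patients (1-10 and 11-20) with randomization ratio of 1:1 in each group", hence 5 + 5 = 10 per arm) and the 0.05 significance level in section 8.1, taken as two-sided because the plan does not say.

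The rest is assumed: a normally distributed outcome such as procedure time, no true difference, a t-test, and 100,000 simulated trials. The k longest dusting cases are withdrawn and leave the analysis, and each replacement enters either arm with probability 0.5. In the comparison case the same number is lost at random.

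| k | Type I error | False finding that dusting is faster | Mean bias (SD units) | Type I error, k lost at random |
|---|---|---|---|---|
| 0 | 4.9% | 2.4% | 0.00 | – |
| 1 | 7.4% | 6.1% | -0.16 | 4.8% |
| 2 | 10.8% | 10.1% | -0.28 | 5.0% |
| 3 | 14.5% | 14.1% | -0.38 | 5.0% |

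Simulation error near 5% is √(0.05 × 0.95 / 100,000) = 0.0007, or 0.07 percentage points. Two selective substitutions multiply the error rate by 10.8 / 4.9 = 2.2. Loss unrelated to outcome leaves it at its nominal level, so the harm comes from selection and not from the smaller or uneven groups.

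**The case against.** The strongest reply is that replacement adds a subject and removes no one. No section deletes a withdrawn subject's data, and section 10.4 asks for continued follow-up, so a withdrawn subject who returns at 1 month stays in the analysis. This stands. The loss works through the section 6.1 discard, and the two issues should be handled as one. It does not remove the need to amend section 7.3.3, because open-ended replacement is what restores the count and hides the loss.

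Other replies and what remains of them:

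- **Replacement is conditional.** The sentence in section 7.3.3 covers the case where a dropout is replaced; it does not require it for every dropout. Correct: the point is what the text permits.
- **Withdrawals are documented.** Date, initiator and reason are recorded, and section 8.1 lists reported adverse events. The adverse event listing is therefore not the main worry. But retained records do not settle who enters the performance analysis.
- **The target of 20 and the spare allocations can coexist.** They can. Section 7.3.3 expects additional subjects, and no section sets a dropout and a replacement against each other for one place.
- **Taking the next envelope is sound.** Agreed. Reusing the lost subject's arm would make the replacement's allocation predictable, and an uneven split is not in itself a bias.
- **The simulation assumes deliberate removal of the worst cases in one arm.** It does, and it is an upper illustration. Nothing in the documents suggests such intent.

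**Conclusion.** The concern holds as a gap in the rules. As written, a treated subject with known procedure time, extraction-device use and often discharge time can leave the performance analysis and be substituted, at the discretion of parties one of whom knows the arm. The size cannot be derived from the documents. Under the worst-case assumptions above, one to three selective substitutions raise the type I error from 4.9% to between 7.4% and 14.5%; if losses are unrelated to outcome, there is no inflation.

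A reader might infer two stronger claims that the documents do not support. The first is that a subject with complete data can be swapped out. Participation ends at the 1-month visit, and section 6.1 discards only those who have not attended it. The second is that 1-month clearance can be improved by withdrawing subjects known not to be cleared. That result does not exist at an earlier withdrawal. The surgeon's stone-free judgement at the end of surgery (section 7.6.3) does, but it is not the primary endpoint.

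**What to change.** - **Section 7.3.3:** state that only subjects who leave before lithotripsy starts may be replaced. Keep the next-envelope rule.
- **Sections 6.1 and 10.4:** state that any subject in whom the laser was fired stays in the randomized arm for every endpoint already collected, whoever initiated the withdrawal and whether or not the subject returns at 1 month. Only the 1-month imaging is then treated as missing.
- **Reporting:** show all randomized subjects by arm in a flow table, with replaced subjects and their reasons. Since allocation takes place at enrollment, exits before lithotripsy should be listed by arm too.

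Make these changes together with the revision of the section 6.1 discard rule, since that is how the data are lost. The cost is a few sentences and one table; neither treatment nor the planned number changes. The downside is that the number with 1-month imaging may fall slightly below 20.

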### 7.4 Pre-treatment evaluation

The following examinations are included in the standard of practice for subjects with renal calculi and may have been performed prior to the subject enrollment. Medical history as well as measurements that were completed prior to study enrollment will be used as baseline data for the study.

- A complete history and physical examination and total duration of the patient's symptoms;
- Blood and urine tests including urinalysis, urine cultures, complete blood count (CBC).
- Stones sizes and locations measured using the most recent X-ray or abdominal Computed Tomography imaging performed.

### 7.5 FURS pre-operative preparations- according to hospital routine of care

#### 7.5.1 Anesthesia

The subject will be put under regional (spinal) anesthesia or general anesthesia, per standard hospital practice for FURS procedures.

#### 7.5.2 Preoperative antibiotics

The subject will be given intravenous preoperative antibiotics per standard hospital practice.

#### 7.5.3 Retrograde guide introduction

The subject will be placed in the dorsal lithotomy position. A cystoscope will then be inserted through the urethra into the bladder. If a prior ureteral stent is present the vesicle end of the ureteral stent will be removed outside the external urethral meatus, a guidewire will be inserted through its lumen up to the renal pelvis (under fluoroscopy). A ureteral catheter will then be used to perform retrograde pyelography under fluoroscopy. If no previous stenting was performed ureteral catheterization of the treated side will be performed and guide introduction to the kidney will be performed under fluoroscopy through the ureteral meatus as commonly performed.

This part of the procedure is complete when at least one guidewire is left in place. This guidewire will remain throughout the procedure as a safety measure.

#### 7.5.4 Ureteral dilation and access sheath

If ureteral dilation is needed, mainly when ureteral stenting wasn't performed prior to the surgery, it will be performed using consecutive ureteral dilators or ureteral balloon dilator per standard hospital practice.

Introduction of a ureteral access sheath will be introduced per standard hospital practice.

### 7.6 FURS procedure

A flexible ureteroscope will be inserted over a guidewire to the kidney, with or without a ureteral access sheath, as needed. Renoscopy will then be performed and all calculi will be localized.

#### 7.6.1 Fiber introduction

After the stones are visualized, the 200 DFL fiber is introduced through the scope (either partially deflected or fully deflected, till visible in the end of scope).

#### 7.6.2 Lithotripsy

Lithotripsy will be performed using the Lumenis Pulse 120H holmium laser system and the 200 DFL ball tip fiber using the suggested parameter range sets listed below. The treatment set used will be predefined according to the treatment group the subject was randomized to.

Task	Group I (stone breaking)	Group II (stone dusting)
Energy per pulse	1 - 2.0 J	0.2 - 0.5 J
Frequency	10 – 30 Hz	70 – 80 Hz
Maximum power possible	40 W*	40 W*

- Do not exceed the maximum 40W energy

#### 7.6.3 Stone clearance

In all stages of the procedure, stone fragments extraction may be assisted, if needed by the use of baskets, forceps or saline flushing. Use of such accessories will be recorded.

At the end of stone fragmentation procedure, the renal pelvis will be inspected again and a "stone-free status" will be determined by the surgeon. Remnant fragments of 1 mm will be included under the "stone-free status" category. Complete stone clearance will be confirmed by intraoperative fluoroscopy. Finally, the ureter will also be inspected ureteroscopically and fluoroscopically with the administration of contrast medium to detect possible urine extravasation and remnant stone fragments.

#### 7.6.4 Stent placement

A double-J ureter catheter may be introduced, per standard hospital practice.

### 7.7 Follow - up Regimen

Each subject will be evaluated by the physician post the procedure as per standard of care to assess subject wellness. Subjects will be released from the hospital per the hospital standard practice. Each subject will return one month following the procedure for a follow-up visit to assess stone clearance and subject well-being. Evaluations during each of these visits will be performed as described in Table 1. Additional unscheduled visits or examinations performed that are not part of the standard of care will be recorded in a dedicated Case Report Form (CRF).

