### 5 Outcome Measures

#### 5.1 Primary Endpoints

- Procedure time
- Usage of alternative stone extracting devices
- Catheterization time
- Time to hospital discharge
- Stone clearance based on 1 month follow-up imaging data

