#### 7.2.1 Objective Measures

- 7.2.1.1 Blood workup: including CBC & BMP
- 7.2.1.2 Urine workup: including urine analysis and urine culture (if applicable)
- 7.2.1.3 Renal stone size and location will be performed using Computer Tomography
- 7.2.1.4 All imaging verifying the diagnosis, pre-intervention images, intra-operative (during laser activation) images, immediate post-operative and follow-up images and relevant fluoroscopy and CT images will be recorded on electronic media for documentation, further analysis and data recording.  
Subject anonymity will be assured for all images by deleting any ID detail. Only the code for the Case Number in the study will appear on the records being transferred to the sponsor.
- 7.2.1.5 Stone clearance status will be confirmed one month post discharge using non contrast abdominal Computed tomography (for Radiolucent calculus) or KUB X-ray combined with kidneys and bladder Ultrasound imaging (for radiopaque calculus).

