### 7.3.2 Subject Identification

At enrollment, each subject will receive an identifying number that will include a consecutive serial number. The subject identification number and the subject initials will be used to identify the subject during the entire study and will be entered in the subject's CRF for each treatment and photographs.

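### The plan does not say who reads the 1-month images for the stone-clearance primary endpoint, whether that reader is masked to arm, or what residue counts as clear

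*Combined protocol and SAP*

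**What the plan says.** Section 5.1 lists among the primary endpoints "Stone clearance based on 1 month follow-up imaging data". Section 7.7 gives the occasion: "Each subject will return one month following the procedure for a follow-up visit to assess stone clearance and subject well-being". Section 7.2.1.5 gives the method: "Stone clearance status will be confirmed one month post discharge using non contrast abdominal Computed tomography" for radiolucent stones, or KUB X-ray with ultrasound for radiopaque ones. None of these names a reader.

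Section 7.2.1.4 requires pre-intervention, intra-operative, post-operative and follow-up images to be kept; they "will be recorded on electronic media for documentation, further analysis and data recording". It adds "Subject anonymity will be assured for all images by deleting any ID detail" and "Only the code for the Case Number in the study will appear on the records being transferred to the sponsor". Section 7.3.2, on the other hand, says "The subject identification number and the subject initials will be used to identify the subject during the entire study".

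On knowledge of the arm, 7.3.3 has the sponsor supply sealed envelopes that contain the treatment parameters, and 7.6.2 ties the laser settings to the allocated group. Section 10.5 makes the investigator responsible for recording the study data on the CRFs. Section 6.1 specifies one site and 20 subjects drawn from the physician's own patients.

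Section 7.6.3 counts 1 mm remnants as stone-free, but for the surgeon's inspection at the end of the procedure. No section available for review mentions masking, an independent reader, or a fragment threshold at 1 month.

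**The concern.** The person who operates cannot be masked, because the allocation is the laser setting. Four of the five primary endpoints (procedure time, use of extraction devices, catheterization time, time to discharge) arise during care by staff who may know the arm. Stone clearance is different: it is read from an image taken a month later, and that read can be separated from the operating team. The plan does not use this, and it leaves open that the operator decides the result.

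Two features make the read sensitive to expectation. First, the rationale in 1.2 and 9.3.3 expects dusting to leave fine particles that wash out without retrieval, so how small residue is judged bears directly on the comparison. Second, no threshold says what residue counts as clear at 1 month, so the reader sets the standard case by case. The stated objective, to demonstrate the efficiency of dusting, points in one direction.

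Clearance is also the primary endpoint that most directly shows whether a shorter procedure left stone behind. A read that favours one arm would distort that comparison.

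**Working it through.** **1. The sections side by side.**

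| Question | What the plan gives |
|---|---|
| Is 1-month clearance a primary endpoint? | Yes (5.1) |
| When is it assessed? | 1-month visit (7.7) |
| By what imaging? | CT, or KUB X-ray plus ultrasound (7.2.1.5); CT and/or X-ray (Table 1, Appendix I) |
| Who reads it? | Not stated |
| Is the reader masked to arm? | Not stated |
| What residue counts as clear at 1 month? | Not stated; 1 mm only at end of procedure (7.6.3) |
| Who knows the arm? | The operator, necessarily (7.3.3, 7.6.2) |
| Who enters the result? | Responsibility lies with the investigator (10.5) |

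Nothing in the table keeps the operating investigator from deciding the endpoint.

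**2. Does 7.2.1.4 already provide masking?** No. It removes identity, for anonymity, from records sent to the sponsor. The sponsor also supplies the envelopes, so someone there might link a case number to an arm. The stored set includes images taken during laser activation. Section 7.3.2 keeps subject initials as an identifier.

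**3. Scale.** The plan states no clearance rate, power or effect size, so there is no figure of its own to reproduce. Inputs: 20 subjects (6.1); 1:1 allocation within subjects 1-10 and 11-20 (7.3.3); significance at p < 0.05 (8.1). Subjects per arm = 20/2 = 10. One changed read moves an arm's rate by 1/10 = 10 percentage points.

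**4. A boundary case.** Section 8.1 names tests for continuous variables only. Two-sided Fisher's exact test is my assumption. With 10/10 cleared in one arm, the two-sided p is twice the probability that all the failures fall in the other arm:

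- 10/10 against 6/10: 2 × C(10,4)/C(20,4) = 2 × 210/4845 = 0.087.
- 10/10 against 5/10: 2 × C(10,5)/C(20,5) = 2 × 252/15504 = 0.033.

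One read crosses 0.05 here, but only where a gap of 40 to 50 points already exists.

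**5. Illustration of bias.** Assume the same true clearance p in both arms, from 50% to 90%, and a misreading share m from 10% to 30%. Rejection is by Fisher's test at 10 per arm.

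- *No misreading:* rejection is 0.1% to 1.3%.
- *One direction:* a share m of dusting subjects with residue is called clear. The spurious difference is m(1 − p), from 0.1 × 0.1 = 1 point to 0.3 × 0.5 = 15 points. Rejection is 0.1% to 3.4%.
- *Both directions:* a share m of cleared breaking subjects is also called not clear. The spurious difference is m(1 − p) + mp = m, that is 10 to 30 points. Rejection is 1.1% to 15.6%; it passes 5% at m = 20% (5.4% to 6.0%) and is 12% to 16% at m = 30%.

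One-directional misreading therefore mainly biases the estimate and does not push the false-positive rate above 5%. The documents give no basis for choosing m.

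**The case against.** The strongest reply is that the plan does not say the investigator reads the images. In 7.7 the physician's evaluation belongs to the sentence on well-being after the procedure; the 1-month sentence names no assessor. Clearance stands under objective measures in 7.2.1, apart from the investigator's subjective assessments in 7.2.2, and a routine radiology report is not ruled out. This stands. A reader might infer that clearance is judged by the investigator, open-label, but the documents do not say so. What they support is that this outcome is left open.

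A reader might also infer that the images are already masked by their coding, so that a masked read would cost next to nothing. The documents do not support this either: the coding serves anonymity, and no section bears on cost.

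Third, the figures could be called selective. This stands in part. Fisher's test is not in the plan, the boundary example presupposes a large gap, and only misreading in both directions at about 20% or more takes false rejection past 5%. Clearance is also one of five primary endpoints with no joint success rule, in a small and largely descriptive study, so it would go too far to say that the whole conclusion falls with it.

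Finally, masking has limits. If the two settings leave visibly different residue, a masked reader may guess the arm, and a re-read of stored ultrasound does not mask the person who acquired it. These limits stand. They argue for a clear fragment rule and a neutral imaging request as well as a masked reader.

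**Conclusion.** The concern holds as a gap with a practical remedy. For a primary endpoint read from an image, the plan names no reader, provides no masking to arm and sets no residual-fragment rule; as written, the operating investigator may decide the result. The documents do not show that this will happen, or that any read would be biased.

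In size, one read is worth 10 percentage points in an arm of 10. The bias range in the working rests on assumed clearance rates, assumed misreading shares and Fisher's test, and serves only to show scale. The main risk is a distorted clearance estimate. The point is worth settling before the first 1-month visit, because results entered by someone who knows the arm cannot be cleanly repaired afterwards.

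**What to change.** In 7.2.1.5 and 7.7, state that:

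- the clearance result for the primary endpoint is taken from the hospital's routine read of the 1-month imaging;
- the reader did not take part in the procedure and has no access to the allocation, the laser settings or the intra-operative images;
- the imaging request carries neither the treatment arm nor the settings;
- the residual-fragment rule for this read is fixed in advance, by the clinical team, for each imaging method used;
- the operating investigator's own impression is recorded separately and is not the endpoint.

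No access is the right condition; not having been told the arm is weaker, since a hospital reader could otherwise look at the treatment record.

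The imaging is already required, so no examination is added, and no extra reader is needed if the routine read is used. The cost is a few sentences in two sections, a change to the request form, and entry of the result from the imaging report rather than at the visit. Masking of the person who acquires the ultrasound will still depend on that form.
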